1.4 Study Design

This study is a double-blind, placebo-controlled, two-arm trial in which 120 binge drinkers with AUD will be randomly assigned to receive 12 weeks of kudzu or placebo, to be taken on an as-needed basis (see Figure 2) with 1- and 3-month post-treatment follow-up visits. This efficacy study will enroll sexually active, binge drinkers with AUD because they are the most likely population to benefit from this intervention by limiting harms associated with heavy alcohol use and decreasing alcohol-related sexual risk behaviors. A study clinician will perform the Structured Clinical Interview for the DSM-V (SCID) to screen for AUD and determine eligibility. Upon enrollment, 120 participants will be randomized 1:1 to kudzu extract (2 grams) or placebo for targeted administration. Participants will be seen weekly for behavioral surveys, urinalyses, study drug dispensing, and alcohol use counseling. Safety laboratory assessment, vital signs, and the audio computer assisted survey instrument (ACASI) will be completed monthly. Efficacy, tolerability, and acceptability (Specific Aims 1-4) will be assessed upon trial completion as measured by number of binge drinking occasions and numbers of drinks on drinking days via timeline follow-back at weekly visits; number of EtG-positive urine samples; sexual risk behavior data through monthly surveys via ACASI; frequency of adverse events; and cumulative medication adherence data at week 12. Durability of intervention effects will be evaluated at 1- and 3-month post-treatment visits.

1.4.a. Study Participants, recruitment, and inclusion/exclusion criteria. We will recruit a total of 120 racially/ethnically diverse sexually active, binge drinkers with AUD will be enrolled in the study. Subjects will be San Francisco Bay Area residents between 18-70 years of age. The project is designed specifically for binge-drinkers at high risk for HIV transmission or acquisition.

1.4.b. Recruitment.

For this study, we will combine several strategies that have proven successful in our previous studies with alcohol- and substance-using individuals:

Advertisements: We will run advertisements in the local papers catering to the community and widely read by our participants.

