First, study staff will be trained to be alert for any factors that signal a low likelihood of the participant being able to adhere to the study schedule; for example, participants who are unable to provide contact information or who miss or re-schedule screening visits are retention risks. Whether or not to enroll such persons will be determined on a case-by-case basis.

We will use a variety of up-front and long-term strategies from our prior studies to achieve excellent retention rates. At screening, participants will be asked to provide extensive locating information, including home addresses, cell and home phone numbers, and e-mail addresses for themselves, and to provide the names of two local persons to be contacted in the event that the participant cannot be reached. We will attempt to contact persons on this list only in the event that multiple attempts to reach the study participant directly fail; at no time will we divulge information about the study or the participant to these contacts. Contact information will be updated every four weeks, or more frequently as necessary. We have found these procedures to be highly acceptable to participants.

We have also found that scheduling out appointments in advance is useful for helping participants to understand the frequency of visits and for maintaining higher retention rates. This is easily done using our Wellsky® appointment scheduling software. Each participant is also provided with a wallet-sized appointment card containing study staff contact information. Future appointments are reviewed and rescheduled as needed. For missed or canceled visits, we contact participants by their selected form of communication (home telephone, cell phone, e-mail, text message, etc.) within 24 hours to reschedule by making up to three attempts to contact individuals at different times of day. We will also attempt to reach up to two alternate contacts provided by the participant at enrollment.

1.4.d. Inclusion Criteria.

Subjects must meet *all* of the following inclusion criteria to be eligible for participation in this study:

1. Self-reported anal or vaginal sex in the prior three months while under the influence of alcohol, or reported missing ART or PrEP due to alcohol use in the prior 3 months; ;
2. At least one binge-drinking (five or more drinks on a single occasion for men; four or more drinks for women) session per week in the prior three months;

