As with our study, participants will receive daily Ecological Momentary Assessments (EMA) to collect data on alcohol consumption, number of drinks on drinking days, targeted medication administration prior to anticipated drinking sessions, and sexual risk behaviors.. Participants will be trained on texting procedures, will receive a reference guide during enrollment, and will be encouraged to regularly delete texts and encrypt their phone with passwords for privacy. Participants will be compensated \$1 per day for their time in responding to daily texts, or up to an additional \$7 each week.

1.1.f. Urinalysis for novel alcohol biochemical markers for recent alcohol use

Urine samples will be collected weekly and tested for ethyl glucuronide (EtG) to determine recent alcohol consumption in the past three days. EtG is a relatively novel, highly sensitive indicator for recent alcohol consumption; this alcohol biomarker is detectable in urine for approximately 72 hours.¹⁷⁰⁻¹⁷³ The PI and Co-I, [name], have used EtG to evaluate the efficacy of another pharmacologic intervention in reducing alcohol consumption in a trial funded by the Department of Defense.¹⁷⁴ Urine samples will be tested via liquid chromatography-mass spectrometry through the Redwood Toxicology Laboratory, Inc., the same lab used by [name] and [name] in their ongoing pharmacologic trials to treat AUD. EtG quantitative results will be dichotomized using established cutoff values to distinguish between positive and negative specimens.^{171,173} Whenever possible we will schedule weekly visits on Mondays and Tuesdays, given that binge drinking is likely to be more common during weekends.

1.1.g. Behavioral survey measurements.

Table 4 (page 7) summarizes the data source and collection schedule for the study measures. Standardized and validated behavioral measures^{152-155,163,164,167} will be assessed using audio computer administered surveys (ACASI) to minimize underreporting of risk activities and standardize data collection.^{152,153} To minimize potential social desirability bias, staff will not have access to data during the trial.

1.7. Statistical Plan and Data Analysis.

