We will use generalized estimating equations (GEE) to estimate treatment effects on repeated study outcomes. Primary analyses will be by intention-to-treat, without regard to adherence to treatment. In our prior trials, we had excellent retention and visit adherence. Nonetheless, in this high risk population, missing data may be encountered.^{175,176} We will conduct sensitivity analyses imputing all missing urine samples as positive, adjusting for baseline correlates of missingness, and using inverse probability of censoring weights.¹⁷⁷

Aim 1: To determine the efficacy of targeted kudzu versus placebo in reducing binge drinking among sexually active binge drinkers with AUD, as determined by number of binge drinking days in timeline follow-back (TLFB), by treatment arm. GEE Poisson models with robust standard

errors will be used to assess reductions on weekly drinking outcomes. Baseline TLFB results will be included in the analysis. Minimum detectable effects (MDEs): Based on the prior Project iN trial (93% retention), we conservatively estimate that 80% of participants will be retained at 12 weeks. Using estimates based on Project ECHO for the within-subject correlation and over-dispersion of the outcomes, as well as the mean frequency among controls, we estimate that this study will have 80% power in 2-sided tests with a type-I error rate of 5% to detect 28% reductions in numbers of binge drinking occasions, as well as 11% reductions in the average number of drinks on drinking days. In exploratory analyses, we will evaluate the durability of intervention effects on drinking outcomes at 1- and 3-month post-treatment visits.

Aim 2: *To determine the efficacy of targeted kudzu versus placebo in reducing alcohol consumption among non-dependent individuals with AUD*, as determined by the proportion of ethyl glucuronide (EtG) positive urines, by treatment arm. GEE logistic models with robust standard errors will be used to assess reductions frequency of positive urine tests, accounting for within-subject correlation. MDEs: Using the assumptions for retention for Aim 1, as well as estimates based on biomarker data from [name] et al.'s study on topiramate for alcohol use disorders¹⁷⁴ for the within-subject correlation and control group urine positivity rate, we estimate that the study will have 80% power in 2-sided tests with a type-I error rate of 5% to detect 15-24% reductions in the urine positivity rate in the treatment arm.

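### Aim 2 limits weekday variation in urine sampling through scheduling, but the EtG model does not adjust for what remains; a scheduled-weekday covariate is a cheap precision gain of uncertain size

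*Combined protocol and SAP*

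**What the plan says.** Section 1.1.f has urine collected weekly for EtG and notes that "this alcohol biomarker is detectable in urine for approximately 72 hours". It then sets a scheduling preference: "Whenever possible we will schedule weekly visits on Mondays and Tuesdays, given that binge drinking is likely to be more common during weekends".

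Section 1.4.c describes booking appointments ahead and moving them when needed: "For missed or canceled visits, we contact participants by their selected form of communication", with the aim of rebooking. It sets no weekday window for a rebooked visit.

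Section 1.7, Aim 2, gives the analysis: "GEE logistic models with robust standard errors will be used to assess reductions frequency of positive urine tests, accounting for within-subject correlation". No weekday term is named. The sensitivity analyses listed at the start of 1.7 deal with missing data (missing urines counted as positive, adjustment for correlates of missingness, censoring weights). None deals with the day a sample was taken.

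**The concern.** Take an afternoon sample and a 72-hour window. A Monday sample sees Friday, Saturday and Sunday nights. A Tuesday sample loses Friday. A sample on Wednesday or later in the working week loses both Friday and Saturday. If drinking clusters on weekends, as 1.1.f expects for binges, the collection day helps to predict the result. The preference for Monday and Tuesday makes sense only on that view.

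A participant whose regular slot is late in the week then has fewer chances to test positive than one seen on Mondays, for reasons unrelated to treatment. Left out of the model, that difference sits in the error of the arm comparison for one of the primary objectives. At stake is precision that the same data could deliver.

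**Working it through.** **Inputs from the documents**
- Section 1.4: "120 participants will be randomized 1:1 to kudzu extract (2 grams) or placebo", so 60 per arm.
- Section 1.7, Aim 1, reused for Aim 2: "we conservatively estimate that 80% of participants will be retained at 12 weeks", so 60 × 0.80 = 48 per arm.
- Section 1.7, Aim 2: "80% power in 2-sided tests with a type-I error rate of 5% to detect 15-24% reductions in the urine positivity rate".
- Weekly urine over 12 weeks: m = 12 (1.1.f; Table 3 prints a different EtG schedule, so m = 6 is also tried in step 3).

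**Not given, so assumed**
- Aim 2 names a source "for the within-subject correlation and control group urine positivity rate" but prints no values.
- The share of visits on Monday/Tuesday, the size of any weekday effect, and whether weekdays are fixed per participant are also not given.

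**Step 1. The plan's own figure.** Effective n per arm = n·m / [1 + (m − 1)·ICC]. Solve p1 − p2 = [1.960·√(2·p̄·(1 − p̄)) + 0.842·√(p1(1 − p1) + p2(1 − p2))] / √(effective n).
- Control positivity 0.70, ICC 0.1: 576/2.1 = 274.3, detectable relative reduction 16.3%. ICC 0.3: 576/4.3 = 134.0, 23.7%.
- Control positivity 0.80, ICC 0.2 to 0.5: 16.2% to 23.8%.

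The stated 15-24% is attainable, but cannot be strictly reproduced without the inputs.

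**Step 2. How far weekday could move positivity.** Let a be the drinking rate on Friday and Saturday nights and b = 0.23 the rate on other nights. Ignoring person effects:

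| Sample day | P(positive) | a = 0.45 | a = 0.69 |
|---|---|---|---|
| Monday | 1 − (1 − a)²(1 − b) | 77% | 93% |
| Tuesday | 1 − (1 − a)(1 − b)² | 67% | 82% |
| Later | 1 − (1 − b)³ | 54% | 54% |

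**Step 3. Closed-form check.** Let w be the Monday/Tuesday share and Δ the difference in positivity between Monday/Tuesday and other days. The weekday variance is Vw = w(1 − w)Δ², and the remainder is Ve = p(1 − p) − Vw. The adjusted variance of a participant's mean is Ve[1 + (m − 1)·ICC]/m. Without adjustment, add Vw/m if weekday varies by visit, or Vw if it is fixed for the participant. The variance ratio VR is unadjusted over adjusted. Starting from 80% power, adjusted power is Φ(2.802·√VR − 1.960).

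Example: 0.70 against 0.50, w = 0.8, ICC 0.2. Then p = 0.66, Vw = 0.16 × 0.04 = 0.0064, Ve = 0.2244 − 0.0064 = 0.2180, and the adjusted variance is 0.2180 × 3.2/12 = 0.0581.
- Varying weekday: VR = 1 + (0.0064/12)/0.0581 = 1.009; power 80.4%.
- Fixed weekday: VR = 1 + 0.0064/0.0581 = 1.110; power 83.9%.
- Varying weekday with m = 6: VR = 1 + (0.0064/6)/(0.2180 × 2.0/6) = 1.015; power 80.6%.

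Over the assumptions tried, a varying weekday gains 0.1 to 0.5 points (0.70 against 0.50) or 0.7 to 2.3 (0.80 against 0.40). A fixed weekday gains 1.0 to 5.5 points, or 7 to 16 in the extreme case of 0.80 against 0.40 with 20-50% of participants off Monday/Tuesday.

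**Step 4. Simulated GEE logistic models.** Settings: 48 per arm, 12 samples, between-person SD 1.0 on the logit scale, robust SE, night rates as in step 2. The information ratio compares the model with weekday indicators to the model without. The last column puts that ratio into the step 3 power formula.

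| Weekday pattern | Weekend-night rate | Information ratio | Power from 80% |
|---|---|---|---|
| Varies by visit | 45% or 69% | 0.99-1.01 | about 80% |
| Standing slot, 0-20% after Tuesday | 45-55% | 1.02-1.13 | 80.8-84.6% |
| Standing slot, 20-40% after Tuesday | 69% | 1.25-1.36 | 87.9-90.4% |

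Read directly as simulated power, and including 10% after Tuesday for the large contrast, standing slots gain roughly 0 to 6 points (modest contrast) and 7 to 13 (large). These run slightly above the table where unadjusted power starts below 80%.

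A second simulation gave Monday and Tuesday the same positivity. It gained 0.3 to 1.9 points with a varying weekday. With a fixed weekday it gained 1.0 to 2.8 points (moderate effect), or 4.3, 8.8 and 11.0 points (large effect; 10%, 30% and 50% of participants off Monday/Tuesday).

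Type I error was 4.6-5.4% in one set of runs and near 6% in another, in each case much the same with and without the term.

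**The case against.** **The plan already handles weekday.** A reader might infer that the trial ignores it. It does not: the Monday/Tuesday preference is a design control. If every visit fell on those two days, the simulated gain would be only about 0 to 2.5 points. This stands; the gap is in the analysis only.

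**A strong weekday effect is not documented.** Section 1.1.f calls weekend binges likely to be more common and gives no size. EtG registers any recent drinking, not only binges. The 69% against 23% case is an odds ratio of (0.69/0.31)/(0.23/0.77) = 7.5, which nothing in the documents supports. This stands, and is why the result is a range.

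**Rescheduling does not produce the gain.** Moving single visits makes weekday vary within a participant, and over 12 samples that averages out. The gain needs standing slots. Booking ahead (1.4.c) makes them plausible, but the documents do not say that weekdays are fixed.

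**A shortfall against the planned power is not shown.** The stated 80% refers to the model as planned, with inputs from an earlier trial that may already carry weekday noise. This stands: the point is precision left unused, not an underpowered Aim 2.

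What survives is that the model leaves out a covariate that can be fixed at enrolment, costs almost nothing and may help.

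**Conclusion.** The point holds as a low-cost improvement to the Aim 2 analysis. The gain is about zero if weekday varies freely. It is roughly 0 to 6 power points with standing slots and a modest weekend contrast, and about 7 to 13 only when at least 10% of participants are regularly seen after Tuesday and the contrast is large. All of this rests on assumed night rates, slot patterns and between-person spread.

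A reader might also infer that the EtG comparison is biased. The documents do not support that. Randomisation balances weekday in expectation, and the simulated type I error is much the same with or without the term. Only rescheduling that differs by arm would raise a validity question, and nothing in the documents points to it.

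A separate matter remains. A Monday visit missed after a heavy weekend and made up midweek can turn a would-be positive into an observed negative. The missing-data analyses do not see this, because the sample is not missing, and a scheduled-weekday covariate does not correct it. Section 1.4.g says that weekly visits became remote during the COVID-19 period, without saying how the sampling day was then controlled.

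**What to change.** Before unblinding, amend section 1.7, Aim 2:

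1. Add each participant's scheduled visit weekday (Monday / Tuesday / later), fixed when appointments are first booked at enrolment, as a covariate in the GEE logistic model. Treatment cannot affect it. State in advance how a sparse category would be merged.
2. Report the treatment effect as a standardised difference in proportion positive: average the model's predictions over the observed weekday mix under each arm, with a robust or participant-level bootstrap standard error. The target then stays the proportion of positive urines.
3. Report by arm the share of samples actually collected on Monday/Tuesday, including during the remote-visit period.
4. Present any analysis restricted to, or adjusted for, the actual collection day only as a sensitivity analysis. State that actual day is post-randomisation and may depend on drinking, and that a Monday/Tuesday-only analysis drops the very samples that were shifted.

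Cost: SAP wording, two more coefficients and a standard error for the standardised difference. The documents do not define a standing weekday, so it has to be derived from the appointment records. There is no gain if weekday varies freely or nearly all visits fall on one day; the expected loss in those cases is negligible.

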Surrogate measures for hypothesized kudzu mechanisms		
Alcohol physiological effects, mood states and risk behaviors during drinking sessions ¹⁵⁷	ACASI	W
Alcohol subjective effects scale (SES) on intensity of intoxication and of impairment ; Length of subjective effects of first alcohol drink; ¹⁵⁸ Desire for alcohol ¹⁶⁸	ACASI	W
Binge-drinking score from Alcohol Use Questionnaire; ^{159,160} Speed of drinking/drinking rate; ¹⁶¹ Latency/time delay between first and second drink during drinking sessions ¹⁶¹	ACASI	W
Biphasic alcohol effects scale (BAES) for subjective nature of intoxication (stimulation and sedation) ¹⁶²	ACASI	W
Trial process measures		
No. pre-screened, screened, enrolled; visits attended, overall retention; participant satisfaction with trial	Visit database, ACASI	Ongoing M 3
Additional covariates		
Demographics (e.g., age, race, education)	ACASI	E
Alcohol Use Disorders Identification Test (AUDIT) ¹⁶³	ACASI	E, M
Center for Epidemiologic Studies Depression Scale ¹⁶⁴	ACASI	E, M
Brief Symptom Inventory ¹⁶⁵	ACASI	E, M
Severity of Dependence Scale ¹⁶⁶	ACASI	E, M
Visual Analog Scale Craving Scores ¹⁶⁷	ACASI	E, W

Notes: E=Enrollment; M=Monthly; W=Weekly; D=Daily PT=Post-Treatment

than monthly until the shelter-in-place order is lifted. This is for the safety of our participants.

Medications taken 30 days prior to enrollment and while enrolled in the study will be documented on a concomitant medications form.

1.1.b. Potential Risks.

Adverse drug effects: A primary risk of participation in this study is the potential of AEs due to taking kudzu. As part of the informed consent process, participants will be informed of the potential risks of taking kudzu. As an edible plant, the roots, flowers and leaves of kudzu has long been used for a wide range of food recipes and consumed as tea in East Asia.⁶³ Hence, kudzu is believed to be extremely safe for human consumption.

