Aim 3: *To determine the efficacy of targeted kudzu versus placebo in reducing alcohol-associated sexual risk behaviors and incidence of STIs*, by treatment arm, we will use GEE Poisson models with robust standard errors for the four monthly ACASI assessments on numbers of sex partners, HIV-serodiscordant condomless sex partners, condomless sex partners while intoxicated with alcohol, and condomless sex events with serodiscordant partners, including the baseline value. In the event that these outcomes are severely over-dispersed, we will analyze indicators for any self-report of each behavior, using GEE logistic models. We will use GEE logistic regression models to evaluate differences in incidence of STIs between kudzu and placebo arms over time. Incidence will be evaluated as a composite outcome (i.e., any incident STIs), as well as by type (i.e., incident syphilis, gonorrhea, or Chlamydia), and, for gonorrhea and Chlamydia, by site (i.e., urethral, oral, vaginal, or rectal). MDEs: Based on estimates of within-subject correlation and control prevalence from our Project Echo trial, we estimate that the study will have 80% power to detect 32% reductions in numbers of male anal sex partners, 59% reductions in serodiscordant condomless anal sex partners, 48% reductions in condomless anal sex partners while intoxicated with alcohol, and 58% reductions in condomless anal sex events with serodiscordant partners in the treatment arm. In analyses using GEE logistic models, we will have 80% power to detect reductions of 15% for any male anal sex partners, 39% for any HIV-serodiscordant condomless anal sex partners, 40% for any condomless anal sex partners while intoxicated with alcohol, and 31% for any condomless anal sex events with serodiscordant partners in the treatment arm. After accounting for expected loss to follow-up, we will have an estimated 80% power in 2-sided tests with a type-I error rate of 5% to detect reductions of 23-26 percentage points in the incidence of STIs at month 3, depending on the control rates, assumed to be in the range 30-40%, and within-subject correlation of these outcomes, assumed to be 0.1 to 0.3; both inputs were based on data in an ongoing PrEP demonstration project.

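### Aim 2 names no baseline term although urine EtG is scheduled at enrolment; adding it as a covariate is a nearly free efficiency gain of unknown size

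*Combined protocol and SAP*

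**What the plan says.** The Aim 2 paragraph of section 1.7 gives the model in one sentence: "GEE logistic models with robust standard errors will be used to assess reductions frequency of positive urine tests, accounting for within-subject correlation". It names no covariate. The stated detectable effect, at 80% power and two-sided 5% error, is "15-24% reductions in the urine positivity rate in the treatment arm". The control positivity rate and the within-subject correlation behind it are attributed to a topiramate study, without values.

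The EtG row of Table 3 carries the schedule codes E, W-6 and PT. The key reads "Notes: E=Enrollment; M=Monthly; W=Weekly; D=Daily PT=Post-Treatment", so an enrolment sample is planned. The key does not define W-6, and section 1.1.f says that urine is collected and tested weekly.

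Baseline is mentioned for other aims. Aim 1 says "Baseline TLFB results will be included in the analysis". Aim 3 lists its monthly behaviour outcomes and ends "condomless sex events with serodiscordant partners, including the baseline value". The only other baseline adjustment that could reach Aim 2 is among the missing-data sensitivity analyses: "adjusting for baseline correlates of missingness".

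**The concern.** Aim 2 is one of four primary objectives in a 120-person trial, and it is the drinking outcome that rests on a biomarker rather than self-report. A pre-treatment value of the same biomarker is already scheduled. If it predicts on-study results, using it narrows the interval for the arm contrast at no data cost.

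The silence also leaves open how the value would enter. As a covariate it adds precision. As the first repeated outcome record under a single arm term it would pull the contrast toward zero, because that record precedes treatment. If the choice is left until after unblinding, adjusted and unadjusted results can be compared before one is preferred.

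**Working it through.** **Inputs from the documents.** 120 participants randomised 1:1; 80% retention at 12 weeks, so 48 per arm; two-sided 5% error; 80% power; stated detectable reduction 15-24% (relative or absolute is not said).

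**Inputs assumed, because none is given.** Control positivity p; within-subject correlation of the binary result (ICC); number of on-study samples m, taken as 6 or 12; correlation rho_b between the enrolment result and each on-study result.

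**Step 1: the plan's own figure.** Effective number per arm is 48m/(1+(m-1)ICC). With q the treated rate, solve (p-q)/sqrt{[p(1-p)+q(1-q)]/n_eff} = 1.960+0.842, with m = 12:
- p = 0.8, ICC 0.16: n_eff = 576/2.76 = 208.7, relative reduction about 15%.
- p = 0.8, ICC 0.51: n_eff = 576/6.61 = 87.1, about 24%.
- p = 0.7, ICC 0.07 gives about 15%; p = 0.7, ICC 0.31 gives about 24%.

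The stated range cannot be reproduced as a single calculation, but plausible inputs reach it. It is not shown to be wrong.

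**Step 2: gain from the covariate.** For a subject's mean of m samples, r² = m·rho_b²/(1+(m-1)ICC). The standard error is multiplied by sqrt(1-r²), and power becomes Φ[2.802/sqrt(1-r²) - 1.960]. For example, with ICC 0.3, m = 12 and rho_b = 0.3, r² = 12(0.09)/4.3 = 0.251, the SE ratio is 0.865 and power is 89.9%. Gains in points from 80%:

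| ICC | m | rho_b = ICC | rho_b = ICC/2 |
|---|---|---|---|
| 0.1 | 6 | +1.6 | +0.4 |
| 0.1 | 12 | +2.3 | +0.6 |
| 0.3 | 6 | +8.6 | +2.1 |
| 0.3 | 12 | +9.9 | +2.5 |
| 0.5 | 6 | +16.0 | +4.3 |
| 0.5 | 12 | +16.8 | +4.6 |

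Outside this grid, with rho_b = ICC: at ICC 0.3, one sample gives +3.6 and two give +5.5; at ICC 0.5, +9.9 and +12.9. At ICC 0.65 with m = 12 the gain is +19.5. So 17 is where the grid stops, not a bound; the limit from 80% is +20.

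**Step 3: simulation check.** 108 settings, 3,000 trials each under effect and null: p 0.70-0.90, ICC 0.1-0.5, m = 6 or 12, 20% dropout by the last visit plus 5% intermittent missing samples. The analysis was an independence GEE logistic model with a standardised risk difference and robust SE. Change in power from the binary enrolment term:
- Equally predictive: +0.9 to +9.5 at ICC 0.1-0.3; +13 to +17 at ICC 0.5.
- Half as predictive (latent enrolment/on-study correlation 0.5): +0.1 to +2.3; +2.3 to +3.4.
- Enrolment 95-98% positive: -0.5 to +6.4; +1 to +11.
- Near ceiling and half as predictive: -0.7 to +1.7 overall.
- No predictive value: a loss of at most 0.9.

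Rejection under the null was 4.2-6.6% (mean 5.3%) with and without the term.

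**Step 4: the form of entry.** With complete records, one pre-treatment record among m+1 under a single arm term shrinks the risk difference by 1/(m+1): 1/13 = 8% with 12 samples, 1/7 = 14% with 6.

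**Step 5: sparse data.** At 98% enrolment positivity the expected number of negatives is 120 × 0.02 = 2.4, and the chance of none is 0.98^120 = 9%. At 95% the expected number is 6.

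**The case against.** The strongest reply is that this is a preference. The randomised comparison needs no covariate, the plan does not exclude one, and every input to the gain is assumed. All of that stands, and it limits the point to an optional improvement.

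There are also reasons to expect a gain toward the low end. Entry requires "At least one binge-drinking (five or more drinks on a single occasion for men; four or more drinks for women) session per week", and "this alcohol biomarker is detectable in urine for approximately 72 hours", so enrolment results may be nearly all positive. Section 1.1.f steers weekly visits to Mondays and Tuesdays where possible but does not give the day of the enrolment visit, which may therefore capture different drinking. Weekly counselling (section 1.5.f) may change drinking after enrolment. Section 1.4.g describes remote weekly visits during the COVID-19 order, which may leave some participants with fewer urine samples. These points weaken the best case; they do not make the covariate harmful.

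Aim 3 is not clear precedent. Its four monthly assessments with the baseline value included can be read as carrying baseline as an outcome record, and Aim 1 does not state the form either. The dilution in step 4 describes a model that the plan never proposes; it is a reason to state the form, not a flaw found.

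A reader might infer that Aim 2 is biased, underpowered or inconsistent with the other aims. The documents do not support this: type I error is unaffected, the 15-24% figure is attainable, and silence on a covariate is not its exclusion.

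**Conclusion.** The point holds as an efficiency improvement of unknown size. From 80% unadjusted power, with ICC 0.1-0.5 and 6-12 on-study samples, the gain is about 1 to 17 points if enrolment EtG is as predictive as on-study samples and about 0 to 5 if half as predictive. It is about 0 if EtG is half as predictive and also near ceiling; ceiling alone does not always remove the gain. Fewer samples give less, and ICC above 0.5 gives more. The documents cannot say which case applies. The case for acting rests on the asymmetry: a possible gain of several points or more against a loss of at most about 1.

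**What to change.** Before unblinding, amend the Aim 2 paragraph of section 1.7 as follows.

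- **Covariate.** Enter enrolment EtG (positive/negative) as a baseline covariate in the primary GEE logistic model, not as an outcome record under a single arm term.
- **Sparse-data rule.** State a minimum number of negative enrolment results, judged on pooled blinded data. Below it, replace the binary term with one alternative named in advance: the quantitative enrolment EtG value or baseline TLFB drinking, both already collected. Under one assumed latent model, with 95-98% positive and ICC 0.1-0.3, the quantitative value gave +1.2 to +9.1 points if equally predictive and -0.6 to +2.3 if half, so its gain is plausible but not assured.
- **Missing enrolment results.** Keep these participants, using a missing indicator or simple imputation. With 5% missing and an indicator, up to about 1 point of the gain is given back.
- **Estimand.** Report a standardised difference in positivity with a robust interval, because the adjusted odds ratio is conditional on the covariate.
- **Schedule.** Reconcile W-6 in Table 3 with the weekly sampling in section 1.1.f.

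The cost is a few sentences in the plan and no new data.
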